1.7.1 SIMULINES TRANSDUCER OVERVIEW

The Simulines transducers, referred to as DS 4-4.5S and DS 4-3.0S, are capable of delivering two treatment lines simultaneously at the same focal depth.

The energy settings were validated against the conventional treatment in tissue mimicking material, porcine muscle, and in-vivo porcine skin.

The safety of the derived DS 4-4.5S and DS 4-3.0S energy settings was evaluated in a 96 hour porcine survival dosage study by monitoring the animal for evidence of erythema, edema, and contusion on the skin surface after treatment. Each energy setting of each transducer, DS 4-4.5S and DS 4-3.0S, was evaluated by itself and in combination with the other Simulines transducer at the same energy level. The survival data suggested little to no skin surface effects when treating with the derived DS 4-4.5S, and DS 4-3.0S energy settings. Any skin effects resolved within hours which is equivalent to conventional transducers.

Based on this body of data, the DS 4-4.5S transducer, produces TCPs similar in size to the Standard DS 4-4.5 transducer. The DS 4-3.0S transducer produces a line of TCPs that affect a similar amount of tissue compared to the Standard DS 7-3.0 transducer but requires only 20 TCPs versus 23 TCSs with the DS 7-3.0mm transducer.

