6.4.1 ASSESSMENT OF COMPARABILITY OF RANDOMIZED GROUPS AND POOLABILITY OF INVESTIGATIONAL SITES

Summary tables describing the study population will be produced using subjects in the intent-to-treat population by randomized group. The study population will be described in terms of subject disposition, baseline characteristics, and concomitant medications. Subject disposition parameters will include number of subjects enrolled, treated, discontinued, and reasons for discontinuation. Baseline characteristics will include demographics, height, weight, BMI, and medical history.

The primary efficacy endpoint will be summarized by randomized group and investigational site in the observed intent-to-treat subjects. Although enrollment is set at a minimum of 20 subjects per site, if there is some unforeseen event preventing this minimum level of enrollment per site, investigational sites with fewer than 10 subjects will be combined for this purpose. A random center effect and a random center by randomized group (ITT) interaction will be included in the primary statistical model using logistic regression. If the p-value for the interaction term variance component is < 0.15 , the interaction term and the random center effect will be retained in the model and the effect of treatment will be estimated using this model as an additional analysis to the primary objective. If the p-value for the interaction term variance component ≥ 0.15 and the random center effect is < 0.05 , the random center effect alone will be retained in the model and the effect of treatment will be estimated using this model as an additional analysis to the primary objective. If neither is significant, the effect of treatment will not need to be re-estimated using a model that includes random center or center by treatment effects. The study is not powered to find a statistically significant treatment effect if significant center heterogeneity or effect modification is found, the models however, can be used to pool the data to assess the effect of center heterogeneity or effect modification on the estimated treatment effect.

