6.4.3.2 SECONDARY EFFICACY ANALYSES

The secondary efficacy analyses will be performed using subjects in the intent to treat population who have a non-missing assessment for the efficacy parameter at the time point being analyzed. The secondary endpoints are supportive in nature and are evaluated to provide additional information and are not intended to support additional claims. Descriptive statistics may be included in the labelling and for this purpose are defined as number of observations, mean, standard deviation, median, minimum and maximum for continuous variables and number and proportion of observations for categorical variables. The secondary outcomes may additionally be completed for the subset of per protocol patients.

Secondary efficacy outcomes will be:

6.4.3.2.1 Quantitative improvement measurements of submandibular and submental lift at 180 and 365 days post-treatment compared to baseline.

Endpoint: Subject response is defined as $\geq 20 \text{ mm}^2$ reduction in 2D submental area from baseline. The left and right side value at baseline will be averaged to result in the 2D submental area at baseline. The left and right side value at 180 days will be averaged to result in the 2D submental area at 180 days. Similarly, at 365 days. In the event, only either the left or right side data is available, it will be used. Response will be calculated as baseline – follow-up. The evaluator that determines 2D submental area is blinded to follow-up and study group.

Statistical Analysis: A repeated measures model will be used to analyze the data from this objective. The dependent variable will be response (y/n). The independent variables will be study group and day of follow-up. A covariance structure will be used to account for the correlation expected among the repeated observations collected for each subject. The covariance structure that fits the data best, i.e. results in the lowest Schwarz Bayesian Information Criteria (BIC) value all else held constant will be used, among the

unstructured, compound symmetric or auto-regressive types. Statistical significance will be determined using a two-sided $\alpha=0.05$.

6.4.3.2.2 Comparison of improvement in overall lifting and tightening of skin as determined by a masked, qualitative assessment of photographs at 90, 180 and 365 days post-treatment compared to baseline.

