Statistical Analysis: A repeated measures model will be used to analyze the data from this objective. The dependent variable will be change in volume. The independent variables will be study group and day of follow-up. A covariance structure will be used to account for the correlation expected among the repeated observations collected for each subject. The covariance structure that fits the data best, i.e. results in the lowest Schwarz Bayesian Information Criteria (BIC) value all else held constant will be used, among the unstructured, compound symmetric or auto-regressive types. Statistical significance will be determined using a two-sided $\alpha=0.05$.

6.4.3.2.5 Patient satisfaction and patient reported improvement at 90 days post-treatment.

Endpoints: Patient reported satisfaction and patient reported improvement (see Appendix E) at 90 days post-treatment.

Statistical Analysis: The number and percent of respondents to each of the questions and categories will be summarized by study group.

6.4.3.2.6 Comparison of average treatment times using Simulines transducers compared to average treatment times using Standard transducers.

Endpoint: Treatment time as defined as the time treatment started and the time the treatment concluded as captured per the treatment log.

Statistical Analysis: Treatment time will be compared by study group using the Two-sample T-test.

6.4.3.2.7 Comparison of average pain scores using a validated Numeric Rating Scale to assess subjects' treatment-related comfort level with Simulines transducers versus Standard transducers.

Endpoint: Pain as measured using the validated numeric rating scale (Attachment D).

Statistical Analysis: A repeated measures model will be used to analyze the data from this objective. The dependent variable will be pain score. The independent variables will be study group, transducer depth (4.5 mm, 3.0 mm) and treatment location (cheeks, submandibular/submental). A covariance structure will be used to account for the correlation expected among the repeated observations collected for each subject. The covariance structure that fits the data best, i.e. results in the lowest Schwarz Bayesian Information Criteria (BIC) value all else held constant will be used, among the unstructured, compound symmetric or auto-regressive types. Statistical significance will be determined using a two-sided $\alpha=0.05$.

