6.4.3.2.8 Subject Global Aesthetic Improvement Scale (SGAIS) results assessing overall aesthetic improvement at 90, 180 and 365 days post-treatment.

Endpoint: SGAIS as measured at 90, 180 and 365 days post treatment.

Statistical Analysis: The number and percent observed in each category will be reported by randomized group for each follow-up. A repeated measures model will also be used to analyze the data from this objective. The dependent variable will be improved (y/n) with independent variables study follow-up and study group. A covariance structure will be used to account for the correlation expected among the repeated observations collected for each subject. The covariance structure that fits the data best, i.e. results in the lowest Schwarz Bayesian Information Criteria (BIC) value all else held constant will be used, among the unstructured, compound symmetric or auto-regressive types. Statistical significance will be determined using a two-sided $\alpha=0.05$.

6.4.3.2.9 Clinician Global Aesthetic Improvement Scale (CGAIS) results assessing overall aesthetic improvement at 90, 180, and 365 days post-treatment.

Endpoint: CGAIS as measured at 90, 180 and 365 days post treatment.

Statistical Analysis: The number and percent observed in each category will be reported by randomized group for each follow-up. A repeated measures model will also be used to analyze the data from this objective. The dependent variable will be improved (y/n) with independent variables study follow-up and study group. A covariance structure will be used to account for the correlation expected among the repeated observations collected for each subject. The covariance structure that fits the data best, i.e. results in the lowest Schwarz Bayesian Information Criteria (BIC) value all else held constant will be used, among the unstructured, compound symmetric or auto-regressive types. Statistical significance will be determined using a two-sided $\alpha=0.05$.

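### The secondary repeated-measures models fit one arm effect common to all visits, so no arm difference with an interval is planned at Day 180 or Day 365

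*Combined protocol and SAP*

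**What the plan says.** Six secondary analyses in Section 6.4.3.2 use a repeated-measures model.

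- **Lift response (6.4.3.2.1), masked photographs (6.4.3.2.2) and 3D volume (6.4.3.2.4):** "The independent variables will be study group and day of follow-up".
- **SGAIS and CGAIS (6.4.3.2.8 and 6.4.3.2.9):** "The dependent variable will be improved (y/n) with independent variables study follow-up and study group".
- **Pain (6.4.3.2.7):** "The independent variables will be study group, transducer depth (4.5 mm, 3.0 mm) and treatment location (cheeks, submandibular/submental".

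No list contains a product term, and no contrast at a given visit or depth is described. The endpoints themselves are tied to days. The lift section is titled "Quantitative improvement measurements of submandibular and submental lift at 180 and 365 days post-treatment compared to baseline", and photographs, volume, SGAIS and CGAIS are each named at Days 90, 180 and 365. The inference given for these models is a test: "Statistical significance will be determined using a two-sided" 0.05 level.

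The plan does name an interaction where it wants one. In Section 6.4.1, for poolability of the primary endpoint, "A random center effect and a random center by randomized group (ITT) interaction will be included in the primary statistical model using logistic regression".

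On status, Section 6.4.3.2 says: "The secondary endpoints are supportive in nature and are evaluated to provide additional information and are not intended to support additional claims".

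**The concern.** With group and day as the only terms, the model has one group coefficient and holds the arm difference equal at every visit on the model scale. A reader who wants to know how the arms compare at Day 365 gets an average over the visits. A difference confined to the last visit is mixed with no difference earlier, and effects in opposite directions can cancel. Durability of lift is the natural question for the Day 180 and Day 365 data, and the planned models do not answer it visit by visit.

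The pain model has the same structure across depths. There the arms use physically different 3.0 mm transducers: DS 7-3.0 at 7 MHz against DS 4-3.0S at 4 MHz (Table 1.4-1). Section 1.7.1 says that the latter "requires only 20 TCPs versus 23 TCSs with the DS 7-3.0mm transducer". At 4.5 mm both arms use 4 MHz. An arm effect on pain that varies by depth is therefore possible, and the planned model would report only its average.

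**Working it through.** **1. The plan's own figure.** Inputs from Section 6.4.3.1: 73% in both arms, margin 15%, one-sided 0.05, 80% power, unpooled Z-test.

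n per arm = (1.645 + 0.842)² × 2 × 0.73 × 0.27 / 0.15² = 108.3, so 109. Total 218, and 218 / 0.84 = 259.5, so 260. The stated figures reproduce. The plan gives no figure for the secondary models, so everything below rests on assumed effects, with 109 per arm and 73% carried over from the primary endpoint.

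**2. Late loss in lift.** Assume 73% against 73% at Day 180 and 73% against 58% at Day 365.

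*Day 365 contrast:* SE = √[(0.73×0.27 + 0.58×0.42)/109] = √(0.4407/109) = 0.0636. z = 0.15/0.0636 = 2.36. Power at two-sided 0.05 = Φ(2.36 − 1.96), about 65%.

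*Common effect:* on the risk-difference scale the average is (0 + 15)/2 = 7.5 points. With within-subject correlation r between the two binary responses, the variance of a subject's mean is (v₁ + v₂ + 2r√(v₁v₂))/4, where v = p(1 − p). At r = 0.3 this is 0.1281 in the control arm and 0.1430 in the test arm. SE = √(0.2711/109) = 0.0499, z = 1.50, power about 32%. Varying r from 0.2 to 0.5 moves it from 35% to 29%.

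*Simulation* (logistic GEE, exchangeable, group and day only, latent correlations 0.4 to 0.7) agrees: the common effect is significant in 29 to 36% of trials, against 63 to 69% for the Day 365 contrast. At latent correlation 0.5 the fitted common odds ratio averages about 0.68.

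**3. Other patterns.** Control is 73% throughout; simulation as above.

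| Loss at Day 180, then Day 365 | Common effect significant | Day 365 contrast significant |
|---|---|---|
| 0, then 15 points | 29–36% | 63–69% |
| 7.5, then 15 points | 53–64% | 64–67% |
| 10, then 15 points | 63–71% | 67–68% |
| 15, then 15 points | 79–83% | 65–66% |

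The planned model loses clearly only when the divergence is late, and it gains when the loss is constant. The extreme case is a reversal (test arm 83%, then 63%). The fitted odds ratio is then about 1.01, significant in about 7% of trials, while a group-by-day test detects the pattern in about 87% (150 runs, error about ±8 points).

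**4. Pain by depth.** Assume a 1.0-point excess at one depth only, 130 per arm, one score per depth.

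- SD 2.0, correlation 0.5: depth contrast SE = 2.0√(2/130) = 0.248, power 98%. Averaged effect 0.5, SE = 2.0√(0.75)√(2/130) = 0.215, power 64%.
- SD 2.5, correlation 0.7: SE 0.310, power 90%, against SE 0.286, power 42%.

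If the effect is the same at both depths, the average is at least as good. With 0.75 points at each depth, 125 per arm, SD 2, correlation 0.6 and two locations, power is 94% for the average against 91% for the 3.0 mm contrast.

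**The case against.** The strongest reply is that nothing rests on these models. Section 6.2 ties study success to the primary objective alone, and Section 6.4.3.2 calls the secondary endpoints supportive and confines what may enter labelling to descriptive statistics. That stands and sets the weight of the point. The 3D volume data matter least: Sections 2.2 and 4.6 reserve them for marketing.

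Four stronger readings are tempting, and the documents do not support them.

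- **That a late divergence would be invisible.** For SGAIS and CGAIS the plan commits to counts and percentages by arm at each follow-up. Section 6.4 promises descriptive statistics for every variable, though not by arm and visit. What is missing is a planned contrast or interval.
- **That a non-significant average will be taken as showing no difference.** No section says so.
- **That the pain model misses its endpoint.** The endpoint is a comparison of average scores, and a group effect adjusted for depth and location estimates that. A contrast by depth is an additional question.
- **That the device description predicts a depth-dependent effect.** Section 1.7.1 says that the two 3.0 mm transducers affect a similar amount of tissue per line. The differences in frequency and TCP count make such an effect possible, no more.

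It may also be said that the plan never excludes interactions. That is true. The main-effects reading is an inference from the listed variables and from the explicit interaction in Section 6.4.1. If more was meant, the text still needs to say it.

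**Conclusion.** The point holds in a limited form. As listed, the five visit-based models (6.4.3.2.1, .2, .4, .8 and .9) each give one arm effect common to all visits and no arm comparison with an interval at the days that the endpoints name. The cost depends on the pattern. With a 15-point loss confined to Day 365, detection falls from about 65% to roughly 30 to 36%; with a gradual loss the gap narrows or closes; with a constant loss the planned model is the better one. So the averaged effect is worth keeping, and the visit-specific differences are worth adding.

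The figures rest on assumed response rates and correlations and on a GEE fit. Choosing the covariance by BIC suggests that the sponsor has a likelihood model in mind. The 73% base rate is given for the lift response only, and the text does not say whether Day 90 enters the lift model. The structural point depends on none of this. The primary Day 90 analysis and the sample size are untouched.

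**What to change.** - **6.4.3.2.1, .2, .4, .8 and .9:** add a group-by-day term. Report the arm difference with a confidence interval at each named visit, and keep the averaged effect as a further line. State whether Day 90 enters the lift model.
- **6.4.3.2.7:** keep the average arm effect as the stated endpoint. Add a group-by-depth term (optionally group-by-location) and report arm differences with intervals by depth as supplementary output.
- State that the visit- and depth-specific results are descriptive and carry no multiplicity control.

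The cost is a few words in six model specifications and some extra output rows. Visit-specific intervals will generally be wider than the averaged one, and there will be more supportive contrasts: 2 + 3 + 3 + 3 + 3 = 14 by visit, plus those for pain. Data collection, sample size and the primary test do not change.

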5.3 QUANTITATIVE MEASURES

Submandibular/Submentum quantitative measurements calculated as detailed in **Attachment A**, comparing subjects treated using Simulines versus Standard transducers, will be obtained based on 2D study images obtained at follow-up visits post-treatment compared to baseline.

Comparison of improvement data for overall lifting and tightening of skin as determined by a masked, qualitative assessment of photographs obtained at follow-up visits post-treatment compared to baseline as detailed in **Attachment F**.

Secondary effectiveness will be assessed at baseline and 90 days using the validated, Merz Jawline Grading Scale (MJGS) (**Attachment G**) by independent, masked evaluators using photographs obtained at baseline and the 90-day follow-up visit. The evaluators will be trained and qualified on the MJGS by the sponsor and will remain masked throughout the study. The MJGS is an ordinal scale and ratings will be made based on a “snap-shot” at a single point in time and therefore will not be based on a comparison to a pre-treatment photograph.

The Global Aesthetic Improvement Scale (GAIS) (**Attachments B and C**) will be obtained at all post-treatment time points. The GAIS is a 5-point scale that rates global aesthetic improvement from the pre-treatment appearance. The ratings are worse, no change, improved, much improved, and very much improved. It was validated by [name], et al. for this use. In this study, both live observation and photo review are utilized by the clinician (CGAIS) and subject (SGAIS) in order to assign a score. The CGAIS must be performed by the primary investigator, or a qualified study staff member delegated by the PI. Both the CGAIS and SGAIS should be completed in two steps:

- Based on a live assessment of the subject while referring to the subject’s pre-treatment photographs (subjects should be given a hand mirror for this assessment); and
- Based on a comparison of the subject’s pre-treatment photographs to the current post-treatment photographs.

A validated Numeric Rating Scale (0-10) (**Attachment D**) will be used to record subjects’ pain scores during study treatment. Scores will be obtained for each region treated and for each transducer used.

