5.3.2 SECONDARY ENDPOINTS

The secondary endpoints of this clinical trial include:

1. Subject response as measured by quantitative improvement measurements of submandibular and submental lift at 180 and 365 days post-treatment compared to baseline.
2. Comparison of improvement in overall lifting and tightening of skin as determined by a masked, qualitative assessment of photographs at 90, 180 and 365 days post-treatment compared to baseline.
3. Assessment of mean change from baseline to 90 days post treatment on the validated, Merz Jawline Grading Scale (MJGS) by independent masked evaluators.
4. Quantificare 3D imaging of up to 135 study subjects to assess volumetric changes from baseline compared to 90, 180, and 365 days post-treatment.
5. Patient satisfaction and patient reported improvement at 90 days post-treatment.
6. Comparison of average treatment times using Simulines transducers compared to average treatment times using Standard transducers.
7. Comparison of average pain scores using a validated Numeric Rating Scale to assess subjects' treatment-related comfort level with Simulines transducers versus Standard transducers.
8. Subject Global Aesthetic Improvement Scale (SGAIS) results assessing overall aesthetic improvement at 90, 180 and 365 days post-treatment.
9. Clinician Global Aesthetic Improvement Scale (CGAIS) results assessing overall aesthetic improvement at 90, 180, and 365 days post-treatment.

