Endpoint: The proportion of “Improved, correct pre-post selection” out of the total number of responses. The total number of responses includes the number responding “Improved, correct pre-post selection”, “Improved, incorrect pre-post selection” and “No change”.

Statistical Analysis: A repeated measures model will be used to analyze the data from this objective. The dependent variable will be the proportion meeting the endpoint. The independent variables will be study group and day of follow-up. A covariance structure will be used to account for the correlation expected among the repeated observations collected for each subject. The covariance structure that fits the data best, i.e. results in the lowest Schwarz Bayesian Information Criteria (BIC) value all else held constant will be used, among the unstructured, compound symmetric or auto-regressive types. Statistical significance will be determined using a two-sided $\alpha=0.05$.

6.4.3.2.3 Assessment of mean change and ≥ 1 point improvement from baseline to 90 days post treatment on the validated, Merz Jawline Grading Scale (MJGS) by an independent masked evaluator.

Endpoints: Change in MJGS from baseline to 90 days and proportion of subjects with a ≥ 1 point improvement from baseline to 90 days post treatment. Three masked evaluators that will review subject photos and will be blinded to treatment assignment and follow-up.

Statistical analysis: The mean change in MJGS from baseline to 90 days will be compared between study groups using the Two-sample T-test. The proportion of subjects with ≥ 1 point improvement from baseline to 90 days post treatment will be compared using Fisher’s exact test.

6.4.3.2.4 Quantificare 3D imaging of up to 135 study subjects to assess volumetric changes from baseline compared to 90, 180, and 365 days post-treatment.

Endpoints: Change in volume as calculated per the Quantificare 3D imaging system (see Appendix I) from baseline to 90, 180 and 365 days post-treatment. The evaluator that determines Quantificare volume is blinded to follow-up and study group.

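### Mean MJGS change at Day 90 is compared by an unadjusted two-sample T-test although baseline MJGS is collected, and 6.4.3.2.3 names one evaluator, then three, with no stated rule for one value per subject

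*Combined protocol and SAP*

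**What the plan says.** **Evaluators.** The heading of 6.4.3.2.3 reads "Merz Jawline Grading Scale (MJGS) by an independent masked evaluator". The endpoint paragraph under it reads "Three masked evaluators that will review subject photos and will be blinded to treatment assignment and follow-up". Section 5.3.2, item 3, has "Merz Jawline Grading Scale (MJGS) by independent masked evaluators", and section 5.3 has the ratings made "by independent, masked evaluators using photographs obtained at baseline and the 90-day follow-up visit". The synopsis also uses the plural. None of these three places gives a number.

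**Endpoints.** Section 6.4.3.2.3 has two: the change in MJGS, and the "proportion of subjects with a ≥ 1 point improvement from baseline to 90 days post treatment". Section 5.3.2 and the synopsis list only the mean change.

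**Tests.** For the first endpoint: "The mean change in MJGS from baseline to 90 days will be compared between study groups using the Two-sample T-test". For the second: "The proportion of subjects with ≥ 1 point improvement from baseline to 90 days post treatment will be compared using Fisher’s exact test". Neither sentence mentions the baseline grade as a covariate or says how several ratings are combined.

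**Data available.** The Study Overview and Table 3.1-1 both schedule the jawline scale at baseline and at Day 90. Section 5.3 calls the scale ordinal, with each photograph rated on its own.

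**Status.** Section 6.4.3.2 calls the secondary endpoints supportive and not meant for additional claims, but allows their descriptive statistics in the labelling.

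**The concern.** There are two issues of different weight.

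The first is efficiency. Each photograph is graded separately, so rating error enters the baseline grade and the Day 90 grade independently. A subject graded too high at baseline by chance will tend to show more improvement, and one graded too low will show less. Change is therefore correlated with baseline. An unadjusted comparison of change leaves that predictable variation in the error term. The information needed to remove it is already collected.

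The second is specification. The subsection gives two evaluator counts, and the supplied text has no rule that turns three grades into one. The primary endpoint shows that the plan can be explicit here: section 6.4.3.1 averages the left and right areas and says what to do if one is missing. Without a rule for MJGS, the responder percentage could be settled after the ratings are known, and that percentage may be printed in labelling.

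**Working it through.** **1. The plan's own figure.** The documents give no sample size for MJGS. The only one is for the primary endpoint in 6.4.3.1: 73% response in both arms, 15% margin, one-sided 5%, 80% power, unpooled Z-test. It reproduces: 109 per arm, 218 in total, and 218 / (1 − 0.16) = 259.5, so 260. MJGS does not drive this number. I use 109 per arm only as a scale for what follows.

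**2. Evaluator count and rule, side by side.**

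| Place | Evaluators | Rule for one value per subject |
|---|---|---|
| 6.4.3.2.3 heading | one | none |
| 6.4.3.2.3 endpoint text | three | none |
| 5.3, 5.3.2, synopsis | plural, no number | none |
| Attachment G | listed in the contents | text not in the supplied document |

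The singular heading is the outlier. Three is the only number given in an operative definition.

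**3. Gain from ANCOVA.** With 1:1 allocation and a common slope, adjusting a change score for baseline multiplies the variance of the group difference by approximately 1 − ρ², where ρ is the correlation between change and baseline within a group.

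The documents give neither ρ nor rater reliability, so these inputs are assumptions:
- a 0 to 4 ordinal scale;
- latent baseline grade with mean 2 and SD 0.8;
- true improvement with mean 0.5 and SD 0.3;
- rater reliability 0.6 to 0.9, ratings rounded to whole grades;
- the median of three ratings as the subject's grade at each visit.

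In simulation the variance falls by about 16% at reliability 0.6 and about 8% at reliability 0.9. I repeated this and got the same range. The implied correlations are √0.16 = 0.40 and √0.08 = 0.28.

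| | Reliability 0.9 | Reliability 0.6 |
|---|---|---|
| Variance ratio, 1 − ρ² | 0.92 | 0.84 |
| Standard error ratio | √0.92 = 0.96 | √0.84 = 0.92 |
| Unadjusted subjects per arm for the precision of 109 adjusted | 109 / 0.92 ≈ 118 | 109 / 0.84 ≈ 130 |

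The confidence interval for the group difference is about 4 to 8% shorter. The price is one residual degree of freedom: 215 instead of 216 with 218 subjects.

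**4. What the combining rule changes.** Under the same assumed model, the proportion with an improvement of at least 1 point is:

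| Rule | Reliability 0.7 | Range over 0.6 to 0.9 |
|---|---|---|
| One evaluator | 49% | about 49% |
| Median of three | 49% | about 49% |
| Majority of three | 49% | not tabulated |
| Average change at least 1 | 26% | 24 to 28% |
| Any one evaluator | 84% | 78 to 84% |

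Mean change hardly moves: about 0.48 at reliability 0.7 for the single, average and median rules. The rule matters for the responder percentage and very little for the mean change that 5.3.2 lists.

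**The case against.** The strongest case on the other side is that little is broken. The T-test on change is valid in a randomized comparison. The endpoint is supportive, carries no claim and has no part in study success. A reader would take three evaluators from the definition and treat the heading as a slip. The three most natural rules agree on the responder percentage. All of this stands, and it limits the weight of the point. It does not argue against an adjustment that uses data already in hand. The size of the gain does depend on assumed inputs and would be smaller if ratings were very reliable.

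A reader might go further and infer that the two tests would be run on all three ratings per subject as if they were independent, with inflated error rates. The documents do not support that:
- The responder endpoint and Fisher's test are both worded as a proportion of subjects, so stacked ratings would contradict the text.
- Section 6.4.3.2 defines the analysis set as subjects with a non-missing assessment.
- Where the plan expects repeated observations on a subject, as for pain scores or the aesthetic improvement scales, it specifies a repeated measures model. A plain two-sample test here points to one value per subject.

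The T-test sentence does leave its unit unstated, and the neighbouring photograph assessment in 6.4.3.2.2 uses the number of responses as its denominator. That justifies stating the unit. It does not show an intention to stack ratings.

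A reader might also infer that the responder proportion has no defined value at all. That too goes beyond the documents. Attachment G is cited for the scale and listed in the contents, but its text is not in the supplied document and may hold the rule.

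**Conclusion.** The point holds as a free improvement plus a clarification. ANCOVA on the baseline MJGS would lower the variance of the group difference in mean change by about 8 to 16%, assuming rater reliability of 0.6 to 0.9, the rating model set out above, and the median of three as the subject's grade. The contradiction between one and three evaluators is real but clerical. The combining rule is absent from the supplied text. It could shift the responder percentage by tens of points only if a less usual rule were chosen, such as any single evaluator or an average change of at least 1. The primary analysis, sample size and study success are unaffected. The practical stake is the precision of a supportive comparison and a percentage that may appear in labelling.

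**What to change.** In 6.4.3.2.3:

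1. Replace the two-sample T-test on mean change with an ANCOVA of change (or, equivalently for the group difference, of the Day 90 grade), with study group as factor and baseline MJGS as covariate. Report the adjusted difference with its confidence interval.
2. Change the heading to three independent masked evaluators.
3. Define one MJGS value per subject per visit, for example the median of the three ratings, or cite Attachment G if the rule is already there. State that both the mean change and the response of at least 1 point are computed from that value and that both analyses use one value per subject. The median keeps the result on the ordinal scale; another rule is acceptable if it is fixed before the ratings are seen.

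In 5.3.2, item 3, and in the synopsis: add the response of at least 1 point, so that the endpoint lists match the analysis section.

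The cost is wording only. The baseline grade and the three evaluators are already planned, no further data are needed and the sample size does not change. A subject without a baseline grade cannot enter the ANCOVA, but that subject has no change score for the T-test either.
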